6.5.4. Vital Signs

Vital sign measurements include systolic blood pressure, diastolic blood pressure, pulse rate, respiration rate, and body temperature. Each vital sign parameter will be summarized with descriptive statistics by scheduled time point. Change from baseline will be summarized in a similar manner.

Weight at each scheduled time point and change from baseline will be summarized with descriptive statistics by scheduled time point. Weight will be displayed in kilograms. Height, collected only at baseline, will be displayed in centimeters. Body temperature will be displayed in Celsius.

All vital sign data will be presented in by-patient listings.

6.5.5. Electrocardiograms

ECG measurements include HR, RR interval, QT interval and its Fridericia's correction and Bazett's correction, and clinically abnormal findings. QTcF (Fridericia's correction) is calculated as QT/RR^{0.33}. QTcB (Bazett's correction) is calculated as QT/RR^{0.5}. Each ECG parameter will be summarized with descriptive statistics by scheduled time point. Change from baseline will be summarized in a similar manner.

Shift tables will present changes from baseline in ECG interpretation (categorized as normal, abnormal not clinically significant, abnormal clinically significant) to the worst post-baseline result.

In addition, the number and percentage of patients with at least one post-baseline abnormal ECG result in QTcF during on-treatment period will be summarized. Clinically abnormal ECG results in QTcF will be categorized as follows:

Absolute QTcF interval prolongation:

- QTc interval <= 470 ms
- QTc interval >470 480 ms (with baseline QTc interval ≤ 470)
- QTc interval > 480 500 ms (with baseline QTc interval ≤ 480)
- QTc interval > 500 ms (with baseline QTc interval ≤ 500)

Change from baseline in QTcF interval:

- OTC interval increases from baseline <= 30 ms
- OTC interval increases from baseline 30 60 ms
- QTC interval increases from baseline > 60 ms

All ECG data will be presented in by-patient listings.

6.5.6. Physical Examination

The physical examination will be performed during screening period, on day 1 of each cycle of treatment period, at the End of Treatment, and at 30-day safety follow-up.

The physical examination data will be presented in by-patient listing.

6.5.7. ECOG Performance Status

The ECOG performance status score will be obtained during screening period, on day 1 of each cycle of treatment period, at the End of Treatment, and at 30-day safety follow-up. The ECOG performance status scores and the grades from 0 to 5 are described in Table 10:

 Table 10.
 Grade Categories of Eastern Cooperative Oncology Group Score

GRADE	ECOG	
0	Fully active, able to carry on all pre-disease performance without restriction.	
1	Restricted in physically strenuous activity but ambulatory and able to carry out work of a light or sedentary nature, eg, light house work, office work.	
2	Ambulatory and capable of all self-care but unable to carry out any work activities. Up and about more than 50% of waking hours.	
3	Capable of only limited self-care, confined to bed or chair more than 50% of waking hours.	
4	Completely disabled. Cannot carry on any self-care. Totally confined to bed or chair.	
5	Dead.	

The ECOG performance status score will be summarized with descriptive statistics by scheduled time point. A shift table will be presented to display the shift from baseline grade to the worst post-baseline grade.

6.5.8. Pregnancy Test

If the patient is female and of child bearing potential, a serum or urine β -HCG pregnancy test will be performed during screening period, on day 1 of each cycle of treatment period, at the End of Treatment, and at 30-day safety follow-up. Pregnancy test result will be presented in by-patient listing.

6.5.9. Tumor Tissue Biopsy Sample Collection

The archived tumor tissue biopsy samples will be collected during screening period from patients who signed the ICF if available. A patient level listing will be produced to display the tumor tissue sample collection and the results of tumor tissue sample analysis.

6.6. Exploratory Analyses

The exploratory pharmacodynamic/biomarker analyses will be performed using all patients in Pharmacodynamic Evaluable Set. The exploratory biomarkers may include but are not limited to: Any *FGFR* aberrations, p-AKT, p-MAPK and Ki67. Other than FGFR 1 and 2 amplifications, biomarkers data will be interpreted on exploratory basis.

6.7. Pharmacokinetic Analyses

Blood samples will be collected for PopPK analysis including estimation of steady-state exposure such as AUC. The samples will be used to determine concentrations of TAS-120 in plasma.

Total of three PK samples will be collected on Cycle 2 Day 1 (C2D1), within 1 hour prior to dosing and at 2 hours (±1 hour) and 5 hours (at least 3 hours apart from sampling at 2 hours) post-dose. The 3 samples should be collected on the same day. A pre-dose sample may be collected again in case the patient interrupted medication after the pre-dose sample was collected and had C2D1 at a later date. The second pre-dose sample will be recorded as pre-dose sample for C2D1. Detailed analytical procedures will be described in the independent SAP for PopPK.

The listing of TAS-120 plasma concentration will be provided.

6.8. Interim Analyses

The interim analyses will be performed to determine if the futility criterion was met in Cohort 1, 2 and 3, and if the particular cohort should continue. The interim analysis on Cohort 1 will be performed at the time when there are 19 response evaluable patients in Cohort 1. The interim analysis on Cohort 2 will be performed at the time when there are 19 response evaluable patients in Cohort 2. The interim analysis on Cohort 3 will be performed at the time when there are 9 response evaluable patients in Cohort 3.

During interim analyses, the sponsor will review the data and perform statistical analysis to determine if the particular cohort should continue. The interim analyses will be performed on primary efficacy endpoints only.

Because the study is powered for two-stage design (Cohort 1, 2, 3), the overall type I error is controlled for interim analysis. There is no need for type I error adjustment or sample size adjustment. Because this is open label study, there is no blinding/unblinding. Therefore there is no need for maintaining blinding during interim analysis.

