10.2. Planned Interim Analysis

The Sponsor will review the data at the time a cohort has the required number of patients to determine if that particular cohort should continue.

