3.2. Study Endpoints

3.2.1. Primary Endpoint(s)

- ORR, defined as the proportion of patients with a confirmed response of either complete response (CR) or partial response (PR) per Investigator assessment (Cohorts 1, 2).
- CBR, defined as the proportion of patients with a confirmed response of CR, or stable disease (SD) lasting at least 24 weeks, per Investigator assessment (Cohort 3).
- 6-month PFS rate, defined as the proportion of patients who are alive and progression-free 6 months after the first dose of study drug (Cohort 4).

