4.3. Determination of Sample Size

Approximately 168 patients in total may be enrolled in the study.

Please note: the patient numbers given for efficacy analysis are for the response-evaluable population, defined as the subset of treated patients who have measurable disease (or evaluable disease in Cohort 3), who have at least 1 post-baseline disease/tumor assessment, and who have centrally confirmed *FGFR* amplification. If a treated patient is not eligible for the response-evaluable population (for example, because *FGFR* amplification cannot be centrally confirmed or no post-baseline tumor assessment is available), additional patients will be enrolled to ensure the correct number of response-evaluable patients for analysis as described below.

Sample size considerations for **Cohorts 1 and 2** (primary endpoint ORR) are based on a 2-stage Optimal Simon design, comparing a poor response of \leq 15% versus a promising response of \geq 30%, at an approximate 5% 1-sided significance level and 80% power.

- In Stage 1 (futility assessment), enrollment will include 19 patients in each cohort and accrual will continue to Stage 2, if at least 4 (21%) of 19 patients respond (CR or PR).
- In Stage 2, if the Stage 1 futility boundary is exceeded, an additional 36 patients will be enrolled, for a total of at least 55 patients per cohort. In Cohorts 1 or 2, with a total of 55 patients, if the observed ORR is 30.9%, the 95% exact confidence interval (CI) is (19.1%, 44.8%).

Sample size considerations for **Cohort 3** (primary endpoint CBR) are also based on a 2-stage Optimal Simon design. The null hypothesis that the true CBR is 25% will be tested against a 1-sided alternative, which yields a type I error rate of 5% and power of 80% when the true CBR rate is 50%. In the first stage, 9 patients will be treated. If there are \leq 2 patients with clinical benefit (ie, CR or SD \geq 24 weeks) in these 9 patients, the cohort will be discontinued. Otherwise, 15 additional patients will be treated for a total of 24 patients. The null hypothesis will be rejected if \geq 10 patients with clinical benefit are observed in 24 patients.

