5.3. Populations for Analysis

- All Enrolled Population: All patients enrolled in this study
- All Treated Population: All enrolled patients who received at least 1 dose of TAS-120
- **DLT Evaluable Set:** All patients in the All Treated Population in Cohort 4, excluding those for whom the cumulative dose of TAS-120 was <75% of planned TAS-120 dose or the cumulative dose of fulvestrant was <100% of planned fulvestrant dose for reasons other than DLTs in Cycle 1, or who received prohibited concomitant medications or therapies
- Response Evaluable Set: All patients in the All Treated Population who meet Inclusion Criterion #4 (section 4.1 of protocol), have measurable disease (or evaluable disease in Cohort 3), who have at least 1 post-baseline disease/tumor assessment, and have centrally confirmed FGFR amplification. Patients who discontinue due to intolerable toxicity or death prior to the first post-baseline tumor assessment will also be considered evaluable and will be classified as non-responders
- **Pharmacodynamic Population:** All patients in the All Treated Population who have evaluable pharmacodynamic biomarker data.

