5.4. Timing of Analysis

The interim analysis will be performed at the time a cohort (Cohort 1, 2, 3) has the required number of patients to determine if that particular cohort should continue.

The final analysis will be performed when all patients have at least 6 months follow-up. The clinical cut-off date for the final analysis is defined as the date at which all patients either discontinue from the study or have sufficient follow-up (at least 6 months) from the first dosing date of TAS-120 of the last enrolled patient, whichever comes first.

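### The Cohort 3 futility look is triggered by a count of nine response-evaluable patients with no follow-up condition, so it can fall before the 24-week outcomes it judges are known

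*SAP*

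**What the plan says.** **Trigger.** SAP 6.8: "The interim analysis on Cohort 3 will be performed at the time when there are 9 response evaluable patients in Cohort 3". SAP 5.4 is no more specific: "The interim analysis will be performed at the time a cohort (Cohort 1, 2, 3) has the required number of patients". Protocol 10.2 says the same: "The Sponsor will review the data at the time a cohort has the required number of patients".

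**Who is evaluable.** SAP 5.3 requires treated patients who meet inclusion criterion 4 and have evaluable disease, "who have at least 1 post-baseline disease/tumor assessment, and have centrally confirmed FGFR amplification". A patient who dies or stops for intolerable toxicity before the first scan also counts, as a non-responder. The Schedule of Events (Table 1 in both documents) puts the first on-study scan at week 8, give or take one week.

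**What is judged.** SAP 6.8: "The interim analyses will be performed on primary efficacy endpoints only". For Cohort 3, SAP 3.2.1 makes this confirmed CR or "stable disease (SD) lasting at least 24 weeks, per Investigator assessment (Cohort 3"). SAP 6.4.1 requires at least 4 weeks between the two assessments that confirm a CR.

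**The stop rule.** Under SAP 4.3, with 2 or fewer patients showing clinical benefit "in these 9 patients, the cohort will be discontinued". Otherwise 15 more patients are treated, for 24 in all, and the SAP rejects the null hypothesis at 10 or more.

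**Follow-up.** The only minimum is for the last analysis. SAP 5.4: "The final analysis will be performed when all patients have at least 6 months follow-up".

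**The concern.** The event that opens the look and the endpoint applied at it run on different clocks. If the ninth patient becomes evaluable through a week-8 scan without progression, that patient cannot yet have 24 weeks of SD or a confirmed CR. Patients who entered shortly before may be in the same position.

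No passage says whether SD under 24 weeks is then a failure, a benefit or undecided. The type I error of 5% and power of 80% in SAP 4.3 assume that all nine Stage 1 outcomes are known. SAP 6.8 relies on the two-stage design when it says no adjustment is needed.

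At stake is closing a cohort in which the drug works, or passing a futility gate that is weaker than designed. In an open-label study where the sponsor reviews the data, an unwritten counting rule could also be settled after the data are seen.

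**Working it through.** **Inputs.** From SAP 4.3: null CBR 25%, target CBR 50%, Stage 1 n = 9, stop at 2 or fewer, total n = 24. From SAP 4.3 and 6.4.1: reject at 10 or more. From Table 1: first scan at week 8. From SAP 3.2.1: benefit needs 24 weeks of SD. Protocol 10.1 prints a final cut-off of 11; that is a separate discrepancy and nothing here rests on it.

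**Step 1: reproduce the design, all nine outcomes known.**
- Wrong stop at CBR 50% = P(Bin(9, 0.5) ≤ 2) = (1 + 9 + 36)/512 = 46/512 = 0.0898.
- Power = sum over x = 3 to 9 of P(Bin(9, 0.5) = x) × P(Bin(15, 0.5) ≥ 10 − x) = 0.8055.
- The same sum at CBR 25% gives type I error 0.0485. The chance of stopping at CBR 25% is P(Bin(9, 0.25) ≤ 2) = 0.6007.

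The SAP's 5% and 80% therefore reproduce. An exhaustive search also returns this as the Simon optimal design for those inputs.

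**Step 2: pending SD scored as no benefit, CR negligible.** Let k of the nine have under 24 weeks of follow-up, and m = 9 − k. The k patients add nothing at the look, but their true outcome counts in the final 24. A pending patient who has already progressed is a failure either way, so no separate term is needed.
- Wrong stop = P(Bin(m, 0.5) ≤ 2).
- Power = sum over x ≥ 3 of P(Bin(m, 0.5) = x) × P(Bin(24 − m, 0.5) ≥ 10 − x).
- Type I error is the same sum with 0.25 in place of 0.5.

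| Pending k | Wrong stop at CBR 50% | Power | Type I error |
|---|---|---|---|
| 0 | 46/512 = 9.0% | 80.5% | 4.85% |
| 1 | 37/256 = 14.5% | 76.7% | 4.4% |
| 2 | 29/128 = 22.7% | 70.4% | 3.8% |
| 3 | 22/64 = 34.4% | 60.6% | 3.0% |

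**Step 3: pending SD counted as benefit.** Assume a share q of pending patients is in SD at the look; the documents give no figure, so take 50% to 75%. The chance of stopping a drug with CBR 25% is P(Bin(m, 0.25) + Bin(k, q) ≤ 2).
- k = 1, q = 0.50: 0.5 × 0.6785 + 0.5 × 0.3671 = 0.523. At q = 0.75: 0.25 × 0.6785 + 0.75 × 0.3671 = 0.445.
- k = 2: 0.445 at q = 0.50 and 0.289 at q = 0.75.

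The design value is 0.601. In the limit of no stop at all, 10 or more of 24 has type I error 5.47% and power 84.6%.

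**Step 4: how many could be pending.** The documents give no accrual rate, so assume entries g weeks apart. If the look comes 8 weeks after the ninth entry, the patient who entered j places earlier has 8 + jg weeks and is short of 24 when jg < 16. The number pending is 16/g rounded up, to at most 9. If central confirmation or anything else moves the look to 16 weeks after the ninth entry, it is 8/g rounded up.

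| Spacing g | Pending, look at 8 weeks | Pending, look at 16 weeks |
|---|---|---|
| 16 weeks | 1 | 1 |
| 8 weeks | 2 | 1 |
| 6 weeks | 3 | 2 |
| 4 weeks | 4 | 2 |

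With 4 pending, wrong stop is 50.0% and power 46.9%. If the look falls 24 weeks or more after the ninth entry, none is pending.

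**The case against.** The strongest reply is that the stop rule is written in terms of an outcome: patients with CR or SD of at least 24 weeks among the nine. A patient at week 8 has no such outcome, so a sensible team would wait. That reading is open, and it means the power loss follows from one permitted reading and not from a written rule. It does not close the gap. SAP 6.8 fixes a time for the look, the stop is binding, and SAP 5.4 sets a follow-up minimum for the final analysis but not for this one.

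Two further points stand in part. First, the ninth patient may become evaluable through early death or intolerable toxicity, which is already a final outcome; Step 4 covers only the scan-triggered case, and others among the nine may still be pending. Second, accrual is unknown. FGFR2 amplification is rare (about 2% of invasive breast cancers, Protocol 1.1), which suggests slow entry, but about 75 sites are planned (Protocol 3.1). A CR already confirmed at the look would also reduce the loss.

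A reader might infer that Cohorts 1 and 2 have the same defect. The documents support less. The Stage 1 gate there is worded as PR or CR without requiring confirmation (SAP 4.1 and 4.3), while the primary ORR is of confirmed responses. An unconfirmed response could therefore be counted as a non-response at the look, but the text does not settle it.

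**Conclusion.** The point holds for Cohort 3. As written, the look can occur before Stage 1 outcomes are known, and either way of counting pending SD departs from the stated design. Scored as no benefit, one to three pending patients cost about 4 to 20 points of power (80.5% to 76.7, 70.4 or 60.6%). Scored as benefit, with one or two pending and the assumed SD shares, the chance of stopping a drug with CBR 25% falls from 60% to between 52% and 29%. These sizes rest on true CBRs of 50% and 25%, negligible CR, the SAP cut-off of 10, and a number pending that the documents do not let one predict.

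Three stronger conclusions are not supported. The 5% and 80% figures are not miscalculated; they reproduce under the SAP rule. The plan does not say that pending SD is a failure. Material inflation of type I error does not follow: it falls under the first counting and cannot exceed 5.47% under the second.

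**What to change.** Reword SAP 6.8, SAP 5.4 and Protocol 10.2 for Cohort 3:
- Take the stop decision only when each of the first 9 response-evaluable patients has a determined clinical-benefit outcome: a tumor assessment at or after 24 weeks, or earlier PD, death, new anticancer therapy or end of tumor follow-up.
- Allow continuation as soon as 3 patients have qualifying benefit.
- State that ongoing SD under 24 weeks is pending, not a failure, and whether a week-24 scan taken early in its one-week window counts.
- State whether enrolment pauses meanwhile.

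With all nine outcomes determined, power returns to 80.5% and type I error to 4.85%. For Cohorts 1 and 2, state whether the Stage 1 gate counts confirmed responses only.

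The cost is wording, plus a stop decision about 24 − 8 = 16 weeks later than a week-8 look, with an accrual pause or some enrolment beyond nine. It could be later for a patient off treatment without PD. For such patients the Protocol's Schedule of Events keeps the 8-weekly scans, while Protocol 3.2.5 and the SAP's Schedule of Events say every 12 weeks; these passages should be reconciled.

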7. CHANGES IN PLANNED ANALYSIS

There have been no changes to the initially planned analyses as of the finalization of this SAP.

8. DEFINITIONS AND CONVENTIONS FOR DATA HANDLING

8.1. Baseline Period

Baseline evaluations or events will be defined as evaluations or events that occur before the date and time of the first dose of study drug.

If the onset time of event or evaluation time or dosing time is missing or not collected, the following definitions will apply:

- Pre-treatment AEs will be defined as AEs with an onset date prior to but not including the day of the first dose of study drug
- Baseline evaluations (laboratory tests, ECOG performance status and vital signs) will be defined as evaluations with a date on or prior to the day of first dose of study drug (for ECG, assessments on the day of first dose of study drug will not be included in baseline evaluation)

If there are multiple valid assessments, the assessment that is closest to day (and time if collected) of the first dose of study drug will be used as the baseline in the analyses. If multiple assessments are collected on the same date (and time, if collected), the assessment with the latest database entry date (and time, if collected) will be considered as baseline.

8.2. Post-Baseline Period

To allow differentiation as to which study period an Adverse Event occurred, three categories are defined based upon onset date. Adverse Events that had onset dates prior to the first dose of study drug are considered "prior". Adverse events with onset dates on or after the first dose of study drug and within 30 days following the last dose of study drug are considered "on-treatment" or equivalently "treatment emergent". Events with onset dates more than 30 days after the last dose of study drug are considered as "post-treatment". No "subtracting rule" will be applied when an AE occurs both pre-treatment and post-treatment with the same preferred term and grade. AE summary tables will be based on on-treatment AEs only. Adverse events with onset dates prior to the first dose of study drug as well as those after the last dose of study drug +30 days will be identified in the data listings.

8.3. AESI Definition and Conventions

The AESI consist of a list of preferred terms grouped by specific category (for example, pulmonary events, gastrointestinal events categories) and/or by subcategory (for example, diabetes). These categories and subcategories are defined based on MedDRA, and the list that is most current at the time of analysis will be used. Also, changes may be made to this list with each new version of MedDRA.

8.4. Time-to-Onset Definition

Time-to-onset of AESI (any grade) for a specific category (for example, pulmonary events, gastrointestinal events) is defined as the time between the day of the first dose of study drug and the onset date of the earliest AESI (of any grade) in this category.

If the subject did not experience an AESI (of any grade) in the category, time-to-onset will be censored at the maximum follow-up time of that subject (that is, for subjects without an event, time-to-onset will be censored at last dosing date +30 days if subjects are off treatment and followed for at least 30 days, otherwise it will be censored at the last known alive date.). If subjects experience AESI for a specific category but with event start date after the last dosing date +30 days, time-to-onset will be censored at last dosing date +30 days. The resulting Kaplan-Meier plot will represent the cumulative rate of the AESI (any grade) in the category over time.

Time-to-onset of AESI (Grade 3-5) for a specific category is defined similarly but restricted to Grade 3-5 AESI.

Time-to-onset of drug-related (Grade 3-5 or any grade) AESI for a specific category is defined similarly but restricted to drug-related AESI.

Time-to-onset for a specific subcategory is defined similarly but restricted to events in this subcategory.

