6.5.2.6. Adverse Events of Special Interest

Incidence

Adverse event of special interest (AESI) will be summarized:

- Summary of AESI with the number and percentage of patients reporting AESI, serious AESI, grade ≥ 3 AESI, AESI leading to study drug discontinuation, interruption and dose reduction, and AESI with outcome of deaths.
- Summary of AESI by worst CTC grade (grade 1, 2, 3, 4, 5, any grade, Grade ≥ 3) presented by category or subcategory / PT

A by-patient listing of AESI will also be provided.

Time to Onset

Time-to-onset of selected AESI (e.g. hyperphosphatemia) will be graphically displayed using the Kaplan-Meier technique.

- Time-to-onset of any grade AESI
- Time-to-onset of Grade >3 AESI

The derivation of time-to-onset of AESI is detailed in Section 8.4.

Time to Resolution

Time-to-resolution of selected AESI (e.g. hyperphosphatemia) will be summarized.

• Time-to-resolution of Grade ≥3 AESI

The following summary statistics will be reported: percentage of subjects who experienced the specific events, percentage of subjects with resolution of the AESI (clustered), median, 1st quartile and 2nd quartile of time-to-resolution along with 95% CI (derived from Kaplan-Meier estimation) and ranges.

Time-to-resolution of Grade ≥3 AESI (e.g. hyperphosphatemia) will be graphically displayed using the Kaplan-Meier technique.

Time-to-resolution analyses are restricted to patients who experienced the specific events. Collapsing selected AE and derivation of time-to-resolution of AESI is detailed in Section 8.5.

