6.5.2.8. Multiple Events

The following summary tables will be provided:

- A table showing the total number and rate (exposure adjusted) of occurrences for all AEs by SOC and PT
- A table showing the total number and rate (exposure adjusted) of occurrences for AESI by category / subcategory

The exposure adjusted incidence rate per X patient time is calculated as $X \times Y \times$ (total number of unique AEs) / (total exposure time), where:

X = user-specified time factor, X = 1000 or 100

Y = 365.25 for years or Y = 30.4375 for months

For example, Incidence rate per 100 person-years of exposure (IR/100 P-Y) is calculated as 100 x 362.5 x (total number of unique AE count) / (total exposure time in days).

Unique instances of all AEs (that is, after duplicates have been eliminated and overlapping and contiguous occurrences of the same event (same PT) have been collapsed) will be summarized (0 event, 1 event, 2-3 events, \geq 4 events) by PT. Unique instances of AESI will be summarized (0 event, 1 event, 2-3 events, \geq 4 events) by category/subcategory.

Unique instances of all AEs will be listed.

The algorithm of collapsing selected AE records is detailed in Section 8.5.

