8.5. Time-to-Resolution Definition

In order to derive the time-to-resolution, overlapping or contiguous AESI within a specific category will be collapsed into what will be termed "clustered" AESI. For example, if a subject (without pre-treatment AE) experienced an AE from 01 January to 05 January, another AE (with different PT but within same category) from 06 January to 11 January, and the same AE from 10 January to 12 January, these will be collapsed into one clustered AESI from 01 January (onset date) to 12 January (resolution date). Table 11 summarizes key derivation steps for each type of clustered select AEs.

Time-to-resolution of AESI (any grade) for a specific category is defined as the longest time from onset to complete resolution or improvement to the grade at baseline among all AESI clusters in this category experienced by patients. Events which worsened into Grade 5 events (death) or have a resolution date equal to the date of death are considered unresolved. If a clustered AESI is considered to be unresolved, the resolution date will be censored to the last known alive date. Improvement to the grade at baseline implies that all different AE events in the clustered AESI should at least have improved to the corresponding (that is, with same preferred term) baseline grade (or improve to lower grade). Time-to-resolution is defined only for subjects who experienced at least one AESI in the specific category.

The time-to-resolution of AESI (Grade 3-5) for a specific category is defined similarly with an onset date corresponding to a Grade 3-5 AESI.

Time-to-resolution of drug-related AESI (any grade or Grade 3-5) is defined similarly but restricted to drug-related AESI.

Time-to-resolution for a specific subcategory is defined similarly but restricted to events of this subcategory.

Table 11: Derivation of Clustered AESI

Type of clustered select AE	Derivation	
Any grade	Collapse any on-treatment AESI from the same category	
Drug-related of any grade	Collapse any on-treatment drug-related AESI from the same category	
Grade 3-5	Collapse any on-treatment AESI from the same category. Resolution will be based on the onset date of the earliest Grade 3-5 records (clusters with only Grade 1-2 should not be selected)	
Drug-related of Grade 3-5	Collapse any on-treatment drug-related AESI from the same category. Resolution will be based on the onset date of the earliest Grade 3-5 record (clusters with only Grade 1-2 should not be selected)	

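### SAP 8.4 presents a Kaplan-Meier curve that censors at death and at the end of the on-treatment window as the cumulative AESI rate; it overstates the proportion affected unless onset is early

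*SAP*

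**What the plan says.** For patients without an event, SAP 8.4 says "time-to-onset will be censored at last dosing date +30 days if subjects are off treatment and followed for at least 30 days", and "otherwise it will be censored at the last known alive date". The second clause takes in patients who die on treatment or within 30 days of the last dose, although the rule does not mention death. An AESI that starts later is not an event: "If subjects experience AESI for a specific category but with event start date after the last dosing date +30 days", the patient is censored at last dose plus 30 days. SAP 8.4 then interprets the curve: "The resulting Kaplan-Meier plot will represent the cumulative rate of the AESI (any grade) in the category over time". The same definition carries over to Grade 3-5 events, drug-related events and subcategories.

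SAP 6.5.2.6 says where the curve appears: "Time-to-onset of selected AESI (e.g. hyperphosphatemia) will be graphically displayed using the Kaplan-Meier technique". SAP 6.1 also lists AESI onset and resolution among the Kaplan-Meier analyses and takes rates at fixed time points from that estimate, so numerical rates are allowed as well as a graph.

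On resolution, SAP 8.5 states: "Events which worsened into Grade 5 events (death) or have a resolution date equal to the date of death are considered unresolved". Unresolved clusters are censored at the date last known alive. SAP 6.5.2.6 reports Kaplan-Meier quartiles from these data, together with a simple percentage of patients whose event resolved.

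Two other displays do not use Kaplan-Meier: "Summary of AESI with the number and percentage of patients reporting AESI" (SAP 6.5.2.6) and "A table showing the total number and rate (exposure adjusted) of occurrences for AESI by category / subcategory" (SAP 6.5.2.8).

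**The concern.** Under the SAP's own definition, a patient who has died or has passed last dose plus 30 days can no longer have a countable AESI. These are competing events. Censoring them makes Kaplan-Meier treat such patients as still able to have the event at the same rate as those who remain in the window. Its complement is then the onset risk in a hypothetical setting where nobody dies or stops drug, not the share of treated patients affected. Treatment runs until progression, toxicity or another stopping criterion (SAP 4.1), so most patients should leave the window in this way.

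Safety is a secondary objective. A curve labelled as the cumulative rate would sit in the same report as crude AESI percentages that are lower, with nothing to explain the gap. In SAP 8.5, a patient who dies with the event ongoing is censored as though it could still resolve.

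**Working it through.** The documents state no AESI rate, onset distribution or discontinuation rate, so there is no plan figure to reproduce. The check compares the two estimands under stated assumptions.

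**Inputs**
- Window after stopping: w = 30/30.4375 = 0.986 month (30 days from SAP 8.4; days per month from SAP 6.5.2.8).
- Hazard of stopping, mu: assumed exponential, using Cohort 4's design 6-month PFS as a stand-in (SAP 4.3). For 25%, mu = ln(4)/6 = 0.231 per month; for 50%, mu = ln(2)/6 = 0.116 per month.
- AESI hazard, lambda: assumed constant at 0.02 or 0.05 per month, independent of stopping.
- Minimum follow-up at the final analysis: 6 months (SAP 5.4).

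**Formulas**
- 1-KM(t) = 1 - exp(-lambda t).
- Cumulative incidence CIF(t) = [1 - exp(-lambda w)] + exp(-lambda w) x lambda/(lambda + mu) x [1 - exp(-(lambda + mu)(t - w))].

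**One case in full** (6-month PFS 25%, lambda 0.05, month 12)
- 1-KM = 1 - exp(-0.6) = 45.1%.
- CIF = 0.048 + 0.952 x 0.178 x 0.955 = 0.048 + 0.162 = 21.0%.
- Ratio = 45.1/21.0 = 2.15.

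**All cases**

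| 6-month PFS | lambda | Month 6: 1-KM / CIF | Ratio | Month 12: 1-KM / CIF | Ratio |
|---|---|---|---|---|---|
| 25% | 0.02 | 11.3% / 7.5% | 1.50 | 21.3% / 9.3% | 2.30 |
| 25% | 0.05 | 25.9% / 17.6% | 1.47 | 45.1% / 21.0% | 2.15 |
| 50% | 0.02 | 11.3% / 9.1% | 1.24 | 21.3% / 13.2% | 1.62 |
| 50% | 0.05 | 25.9% / 21.0% | 1.23 | 45.1% / 28.9% | 1.56 |

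A simulation of 2,000,000 patients at 6-month PFS 25%, with the hazard set so that 1-KM at month 12 is 20%, gave a cumulative incidence of 8.7%, as the integral does.

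**Dependence on onset time** (ratio at month 12, 6-month PFS 25% and 50%)
- Onset only after month 3, 1-KM 20%: 3.65 and 1.99.
- Onset only after month 6, 1-KM 20%: 5.74 and 2.44.
- Onset confined to the first two months, 1-KM 80%: 1.03 and 1.02.
- Onset confined to month 1: 1.00 in both.

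**Patients left at month 12** (lambda 0.05)
- 6-month PFS 25%: share in the window exp(-0.231 x 11.01) = 7.8%; also event-free 7.8% x 0.549 = 4.3%, or about 1 of 28.
- 6-month PFS 50%: 28.0% and 15.4%, or about 4 of 28.
- Both are before any censoring at the data cut-off.

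**Resolution, an illustration with an assumed 10% dying unresolved.** Of ten affected patients, suppose one dies unresolved before any other resolves, and the other nine all resolve. After the fifth resolution Kaplan-Meier shows 5/9 = 56% resolved, against 5/10 = 50% of those affected. At the end it shows 100% against 90%. The curve is too high throughout, so its quartiles are reached no later than they should be and sometimes earlier.

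**The case against.** The strongest reply is that this is a choice of estimand. Last dose plus 30 days is where the protocol ends routine AE collection (Protocol 8.1.1) and where the SAP ends the on-treatment period. An AESI can still occur later; it is excluded by definition. Under independent censoring, Kaplan-Meier validly estimates onset risk for patients still in the window. That stands, and it is why relabelling would be an acceptable remedy. It does not rescue the sentence in SAP 8.4, which gives the curve a different meaning.

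The objection is also right on scale. The only AESI named for these curves is hyperphosphatemia, and phosphorus is already checked on Day 4 of Cycle 1; if onset is early, the two estimates nearly coincide. Month 12 lies beyond guaranteed follow-up, with a handful of patients at risk. At month 6 the largest gap in the table is 25.9% - 17.6% = 8.3 points. Crude percentages and exposure-adjusted rates are reported anyway.

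Three stronger readings are tempting but not supported:
- A reader might infer that the plotted rates would differ between cohorts merely because progression rates differ. The table shows the opposite: 1-KM at month 12 is 45.1% under either PFS rate, while the cumulative incidence changes from 21.0% to 28.9%.
- A reader might infer that the reported proportion of patients with resolution is overstated. SAP 6.5.2.6 gives that percentage separately, and SAP 8.5 classes events ending in death as unresolved, so it is unaffected.
- A reader might take a twofold overstatement as a property of this trial. It needs an assumed hazard and a proxy for stopping treatment that the plan gives for Cohort 4 only.

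**Conclusion.** The statement in SAP 8.4 is wrong as written. Read as a cumulative rate, the complement of this Kaplan-Meier curve exceeds the proportion of treated patients with a countable AESI whenever death or the end of the window comes first.

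With a constant hazard of 2-5% per month and stopping at 6-month PFS of 25-50%, the overstatement is about 1.2-1.5 times at month 6 and 1.6-2.3 times at month 12. It is roughly 2 to 6 times at month 12 if onset begins only after month 3 or 6, and negligible if onset falls in the first one to two months. These figures rest on exponential stopping, independence of stopping and onset, and hazards that the documents do not supply. The model also gives the 30-day extension to patients who die, which slightly understates the effect.

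The fault is confined to the time-to-onset curves, any fixed-time rates taken from them, and the Kaplan-Meier resolution curve and quartiles. No primary endpoint is touched.

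**What to change.** In SAP 8.4 and 6.5.2.6, estimate the cumulative AESI rate with the Aalen-Johansen cumulative incidence function. Treat death and the end of the on-treatment window (last dose plus 30 days) as competing events. Censor at the data cut-off, loss to follow-up, or withdrawal of consent to follow-up, and print numbers at risk under each curve. State also how new anticancer therapy started within the 30 days is handled, since Protocol 8.1.1 ends AE collection there.

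If Kaplan-Meier is kept, delete the sentence that equates it with the cumulative rate and label the curve as onset risk while in the on-treatment window.

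In SAP 8.5, treat death with an unresolved AESI as a competing event for resolution.

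The cost is SAP wording and slightly more programming; no new data are needed. One consequence should be stated in the report: the cumulative incidence will depend on how long each cohort stays on treatment, so cohort differences in it are not differences in hazard alone.
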